4.2. Exclusion Criteria

Participants who meet any of the following exclusion criteria will not be eligible for enrollment into the study:

Exclusions related to general health:

1. Severe extensive colitis as evidenced by:
 - Physician judgment that the participant is likely to require hospitalization for medical care or surgical intervention of any kind for UC (eg, colectomy) within 12 weeks following randomization
 - Current evidence of fulminant colitis, toxic megacolon or recent history (within last 6 months) of toxic megacolon, or bowel perforation
 - Previous total or partial colectomy
2. Diagnosis of CD or indeterminate colitis or the presence or history of a fistula consistent with CD
3. Diagnosis of isolated proctitis (defined as proctitis with < 10 cm rectal involvement), microscopic colitis, ischemic colitis, or infectious colitis
4. Hospitalization for exacerbation of UC requiring IV steroids within 12 weeks of screening (a single dose of IV steroids given is acceptable)
5. Positive assay or stool culture for pathogens (ova and parasite examination, bacteria) or positive test for *Clostridioides difficile* toxin at screening (If *C. difficile* is positive, the participant may be treated and retested \geq 4 weeks after completing treatment.)
6. Pregnancy, lactation, or a positive serum beta-human chorionic gonadotropin (β -hCG) measured during screening
7. Clinically relevant neurological, endocrine, metabolic (including, but not limited to, hypo- and hyperkalemia), psychiatric, cognitive impairment, alcohol/drug abuse/dependence, or other major

systemic disease making implementation of the protocol or interpretation of the study difficult or would put the participant at risk

8. Have any of the following conditions or receiving treatments that may affect cardiovascular function:
 - Myocardial infarction, unstable angina, stroke/transient ischemic attack, decompensated heart failure requiring hospitalization or Class III/IV heart failure \leq 6 months prior to or during the screening period
 - History or presence of second-degree or third-degree AV block, sick sinus syndrome, or periods of asystole for $>$ 3 seconds without a functional pacemaker
 - History or presence of recurrent symptomatic bradycardia or recurrent cardiogenic syncope

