 - Screening or Week 0/Day 1 pre-randomization vital signs (taken in the sitting position) with a HR $<$ 50 bpm OR systolic blood pressure (BP) $<$ 90 mm Hg OR diastolic BP $<$ 55 mm Hg. Vital signs may be repeated up to 3 times during a visit to confirm abnormal readings
 - Screening or Week 0/Day 1 pre-randomization ECG with PR interval $>$ 200 ms or Fridericia's corrected QT interval (QTcF) \geq 450 ms in men or \geq 470 ms in women
 - Start, stop, change or planned change in dosage of any anti-arrhythmic drugs (Class I to IV) \leq 1 week before screening or within 1 week before or after randomization
9. Forced expiratory volume at 1 second (FEV₁) or forced vital capacity (FVC) $<$ 70% of predicted values and FEV₁/FVC ratio $<$ 0.70 at screening
10. Uncontrolled diabetes as determined by hemoglobin A1c (HbA1c) $>$ 9% at screening, or participants with diabetes with significant comorbid conditions such as retinopathy
11. History of macular edema or retinopathy
12. History of active tuberculosis (TB), history of untreated or inadequately treated latent TB infection, active or latent TB infection at screening (refer to [Appendix 2](#) for details on TB screening requirements and interpretation of test results). The following are EXCEPTIONS to this exclusion criterion:
 - Participants with latent TB, who have been ruled out for active TB, have completed an appropriate course of TB prophylaxis treatment per national/local medical guidelines or WHO guidelines, have a chest radiograph without changes suggestive of active TB infection, and have not had recent close contact with a person with active TB are eligible to enroll in the study. It is the responsibility of the Investigator to verify the adequacy of previous TB treatment and provide appropriate documentation of treatment compliance
 - Participants diagnosed with latent TB at screening, ruled out for active TB and received at least 4 weeks of an appropriate TB prophylaxis regimen may be rescreened for enrollment. Participants will complete their prophylactic regimen during the trial
13. A clinically significant active infection (eg, serious and/or atypical) \leq 28 days prior to randomization, required IV medication \leq 14 days prior to randomization, or that may worsen (in

the opinion of the Investigator) if the participant is treated with a drug having immunosuppressant effects (ie, etrasimod). Fungal infection of nail beds is allowed.

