5. REMOVAL OF PARTICIPANTS FROM STUDY TREATMENT OR ASSESSMENT

5.1. Discontinuation from Study Treatment

A participant's double-blind treatment may be discontinued for any of the following reasons:

- Adverse event that in the judgement of the Investigator and/or Medical Monitor indicate the participant should not continue study treatment
- Participant noncompliance with the protocol or study treatment that is considered significant by the Medical Monitor
- Investigator decision
- Withdrawal by participant
- Lack of efficacy
- Lost to follow-up
- Study termination by Sponsor
- Other, non-adverse event

A participant's double-blind treatment must be discontinued for any of the following reasons:

- Decline in PFT values (FEV₁ and/or FVC) below 50% of the predicted values
- Confirmed diagnosis of clinically significant macular edema
- Confirmed diagnosis of active TB
- Participants who have a cardiovascular treatment-related symptomatic event (eg, chest pain, dizziness, palpitations, lightheadedness, shortness of breath, or syncope) associated with reduction of the HR or associated with clinically relevant ECG changes at any time during the 4-hour monitoring period on Day 1 or Day 2 (as applicable) (Section 9.4.2.1)
- Participants who have not met the discharge criteria ([Table 3](#)) on Day 1 after \geq 4 hours of extended monitoring, or Day 2 by 4 hours postdose
- Pregnancy (Section 9.9.9)

- Suspected drug induced liver injury as defined by the 2009 FDA Guidance for Industry ([FDA 2009](#))
 - ALT or AST $> 8 \times$ ULN
 - ALT or AST $> 5 \times$ ULN for > 2 weeks
 - ALT or AST $> 3 \times$ ULN and (total bilirubin $> 2 \times$ ULN or international normalized ratio > 1.5)
 - ALT or AST $> 3 \times$ ULN with the appearance of fatigue, nausea, vomiting, right upper quadrant pain or tenderness, fever, rash, and/or eosinophilia ($> 5\%$)

Because transient fluctuations of ALT or AST are common, and progression to severe drug induced- liver injury or acute liver failure is uncommon, automatic discontinuation of study treatment upon finding a greater than $3 \times$ ULN elevation of ALT or AST may be unnecessary. If a drug induced-liver injury is identified, refer to Section [16.6](#) for guidance.

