9.3. Screening and Eligibility

Participant eligibility will be assessed based on protocol inclusion and exclusion criteria. All screening evaluations must be completed and reviewed to confirm potential participants meet all eligibility criteria.

Screening procedures must be completed within 28 days prior to receiving the first dose of study treatment ([Table 6](#)). The Screening Period may be extended for participants who require additional diagnostic testing/consults to determine status of either latent TB or *C. difficile* infection. If the participant is planned to be randomized > 28 days from the signing of the informed consent form (ICF), the Medical Monitor should be consulted to see if repeated testing is needed. The 28-Day Screening Period may also be extended on a case-by-case basis to accommodate reasonable delays in specific screening assessments (eg, PFTs, OCT) due to testing availability. The Medical Monitor must be consulted prior to extension in each case.

Participants may have an abnormal laboratory assessment, repeated 1 time only. If additional retests are considered, the ability to repeat the laboratory assessment should be discussed with the Medical Monitor and the outcome of the conversation should be documented.

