9.3.8. Pulmonary Function Test

Pulmonary function tests including FEV₁ and FVC measurements will be performed. In addition, diffusing capacity of the lungs for carbon monoxide (DLCO) measurements will be performed where locally available (sites where DLCO is not available should consult the Sponsor or Sponsor's delegate).

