9.4. Randomization/Treatment Period

9.4.1. Week 0/Day 1: Pre-randomization

At the Week 0/Day 1 visit (Table 6), prior to randomization, a 12-lead ECG in the supine position and resting vital signs in the sitting position (HR, systolic and diastolic BP, body temperature, and respiratory rate) will be collected. Caffeine and/or nicotine are not permitted within 30 minutes prior to BP measurements.

Participants with the following must not be randomized and should be considered screen failures:

- Sitting vital sign assessment: HR < 50 bpm OR systolic BP < 90 mm Hg OR diastolic BP < 55 mm Hg
- 12-lead ECG showing a second-degree or third-degree AV block, periods of asystole > 3 seconds, PR interval > 200 ms, or QTcF \geq 450 ms (men) or QTcF \geq 470 ms (women).

All predose 12-lead ECGs should be obtained prior to blood sample collection.

Participants who continue to meet all eligibility criteria will be randomized as outlined in Section [6.4](#).

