9.9.4. Pulmonary Function Test

Pulmonary function tests will be performed according to the Schedule of Assessments ([Table 6](#)) and includes FEV₁ and FVC measurements. All participants will have PFTs performed at Screening, and Week 12, or at the ET visit. PFTs occurring at the ET visit that are within 4 weeks of the last assessment (eg, Week 12) will only be required if clinically indicated. The 2-Week Follow-Up visit PFT assessment is only required if clinically indicated.

Participants reporting respiratory adverse events such as dyspnea during the treatment period may return at an unscheduled visit for assessment per Investigator discretion; additional PFTs may be performed as clinically indicated.

Participants experiencing a decline in PFT values (FEV₁ and/or FVC) below 50% of the predicted values must be discontinued from study treatment and scheduled for a follow-up visit.

When available, DLCO measurements will also be performed. When DLCO is not available, sites should consult the Sponsor or Sponsor's delegate. These tests will be performed at a qualified pulmonary function laboratory or respiratory department. Please refer to the American Thoracic Society/European Respiratory Society guidelines for standardization of spirometry and single breath determination of carbon monoxide uptake in the lung ([MacIntyre 2005](#), [Miller 2005a](#), [Miller 2005b](#)).

The safety of trial participants and site staff is paramount, so it is at the Investigator's discretion whether PFT can be safely administered to trial participants during the treatment period. The Investigator should evaluate on a case-by-case basis how best to proceed based on the participant's medical history, the Investigator's clinical judgment, and in consultation with the Medical Monitor. All reasonable efforts should be made to ensure safety and adherence to the protocol. When available, spirometry may be conducted at the clinical site instead of at the pulmonary laboratory. If the decision is made that it is not appropriate to conduct PFTs due to the safety concerns (eg, coronavirus disease 2019 [COVID-19] transmission), then this decision and rationale should be appropriately captured in the participant's source documentation. When available and safe (due to lifting of local restrictions, re-opening of local PFT labs, or improved safety conditions) the tests should be conducted as soon as possible and as close to the timepoints as outlined in the protocol.

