9.9.5. Ophthalmoscopy and Optical Coherence Tomography

A complete ophthalmoscopy and OCT will be performed according to the Schedule of Assessments ([Table 6](#)). OCTs occurring at the ET visit that are within 4 weeks of the last assessment (eg, Week 12) will only be required if clinically indicated. The 2-Week Follow-Up visit OCT assessment is only required if clinically indicated. A standard visual acuity chart should be used for the visual acuity assessment. The OCT machine used should preferably not be changed during the study to allow for comparison of central foveal thickness measurements within each participant across timepoints.

Screening visit:

At the screening ophthalmology visit, the eye examination will include:

- Ophthalmologic history
- Best corrected visual acuity measurement (using Landolt C chart)
- Ophthalmoscopy (may include contact lens biomicroscopy to examine the macula and optic disc). A dilated fundus exam should be performed in all participants at the

screening visit and as needed at subsequent visits in participants with significant abnormalities identified on the screening exam.

- Measurement of central foveal thickness by OCT (recorded in micrometers; required for all participants regardless of the results of visual acuity or ophthalmoscopy)
- Slit lamp examination should be performed to establish uveitis disease status (yes/no). Uveitis should be characterized and graded using the Standardization of Uveitis Nomenclature criteria. Participants with active uveitis without macular edema at Screening are eligible to enroll in the study
- If there is a suspicion of macular edema by ophthalmoscopy and increased central foveal thickness by OCT, then additional testing should be considered at the discretion of the ophthalmologist (for example, fluorescein angiogram may be performed). Participants with diagnosed macular edema at Screening should be deemed a screening failure and should not be randomized.
- Optional procedures in case of clinically significant abnormalities on ophthalmic exam may include but are not limited to:
 - Retinal photographs
 - Intraocular pressure

Scheduled post-screening visits:

At the scheduled ophthalmology visit, the eye examination will include

- Best corrected visual acuity measurement
- Ophthalmoscopy (may include contact lens biomicroscopy to examine the macula and optic disc)
- Measurement of central foveal thickness by OCT

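### Exclusion 9 sets no lung-function floor when FEV1/FVC is 0.70 or above, so a participant can be randomised already below the 50% predicted level that triggers a mandatory stop

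*Protocol*

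**What the plan says.** **Entry.** Exclusion 9 (Protocol section 4.2, repeated in the Synopsis) applies to FEV1 or FVC below "70% of predicted values and FEV₁/FVC ratio $<$ 0.70 at screening". The volume condition and the ratio condition are joined by *and*.

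**Stopping.** Section 5.1 lists among the mandatory reasons to discontinue treatment: "Decline in PFT values (FEV₁ and/or FVC) below 50% of the predicted values". Section 9.9.4 repeats it: "Participants experiencing a decline in PFT values (FEV₁ and/or FVC) below 50% of the predicted values must be discontinued". Neither mentions the ratio. SAP 18.7.1.1 lists percent predicted FEV1 below 50% and FVC below 50% as separate markedly abnormal criteria.

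**Other places where a lung limit could sit.**
- Section 9.3.8 says "Pulmonary function tests including FEV₁ and FVC measurements will be performed" and gives no cut-off.
- Section 9.4.1 introduces its Day 1 list with "Participants with the following must not be randomized and should be considered screen failures"; the list covers only vital signs and ECG.
- Exclusion 7 covers major "systemic disease making implementation of the protocol or interpretation of the study difficult or would put the participant at risk". It names no lung condition or value.
- Section 9.3 states "All screening evaluations must be completed and reviewed to confirm potential participants meet all eligibility criteria", but the criteria to be confirmed are those above.

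**Schedule.** Under section 9.9.4 and Table 6, PFTs are done at Screening and at Week 12 or Early Termination; any others depend on clinical indication.

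**The concern.** A low FEV1 or FVC with a preserved ratio is a restrictive pattern, and exclusion 9 does not catch it. Such a participant can enter below the level at which the protocol requires treatment to stop.

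The consequence depends on how the stopping rule is read, and the protocol does not say which reading applies. If it describes a level, the participant meets it on entry and would be stopped at the next PFT. If it describes a fall from above 50% to below, it can never apply to someone who starts below, so the numeric stop does not protect them.

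Other stopping or interruption rules have a matching entry limit:
- Macular edema is a mandatory stop, and section 9.9.5 says "Participants with diagnosed macular edema at Screening should be deemed a screening failure and should not be randomized".
- Active TB and pregnancy are both entry exclusions and mandatory stops.
- ALT and AST are capped at 2.0 × ULN on entry, below every liver stop in section 5.1 (the lowest begins above 3 × ULN).
- QTcF must be below 450 ms (men) or 470 ms (women) on entry; treatment is interrupted above 500 ms.

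What is at stake is individual safety in a drug class for which SAP 18.1.5 treats pulmonary disorders as events of special interest. A minor reporting effect is that a participant who enters below 50% and does not change still counts as markedly abnormal in the by-visit summary of SAP 18.7.1.

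**Working it through.** This is a check of logic; the plan gives no figure to reproduce.

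**Inputs from the documents.** Entry limits of 70% predicted and ratio 0.70 (exclusion 9); stop level of 50% predicted (sections 5.1 and 9.9.4).

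**Assumptions, not in the documents.** Predicted FVC of 4.2 L, which only sets the scale because the rules act on percentages and a ratio. Predicted FEV1/FVC of 0.75, 0.80 or 0.85, needed to express FEV1 as percent predicted.

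**1. The rule as written.** Excluded = (FEV1 < 70% or FVC < 70%) and FEV1/FVC < 0.70. When the ratio is 0.70 or above the second part is false, so no volume excludes.

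**2. Worked example.**
- 70% limit: 0.70 × 4.2 = 2.94 L. 50% level: 0.50 × 4.2 = 2.10 L.
- FVC 2.0 L: 2.0 / 4.2 = 47.6% predicted.
- Exclusion 9 then applies only if FEV1 is below 0.70 × 2.0 = 1.4 L.
- With FEV1 1.6 L the ratio is 1.6 / 2.0 = 0.80, so the participant is eligible although FVC is below the stop level.

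**3. Both volumes can be below 50%.** FEV1 % predicted = FVC % predicted × observed ratio / predicted ratio. For FVC 45% and ratio 0.80:
- predicted ratio 0.75: 45 × 0.80 / 0.75 = 48.0%
- predicted ratio 0.80: 45 × 0.80 / 0.80 = 45.0%
- predicted ratio 0.85: 45 × 0.80 / 0.85 = 42.4%

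**4. Does another reading close the gap?** Three readings were run over FVC 20–120% predicted and ratios 0.30–1.00, counting combinations that are eligible yet have FEV1 or FVC below 50%.

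| Reading of exclusion 9 | Predicted ratio 0.75 | 0.80 | 0.85 |
|---|---|---|---|
| (FEV1 or FVC < 70%) and ratio < 0.70 | 943 | 973 | 1018 |
| FEV1 < 70%, or (FVC < 70% and ratio < 0.70) | 0 | 0 | 0 |
| Any one of the three | 0 | 0 | 0 |

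These are grid points, not frequencies. They show that the gap exists under the first reading only. That is the natural one: FEV1 and FVC share one limit, and the ratio is added by *and*. Exclusion 8 writes OR where its vital-sign limits each stand alone.

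**5. Effect of adding a 50% floor.** Revised rule = current rule, or FEV1 < 50%, or FVC < 50%.

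| Case | Current rule | Revised rule |
|---|---|---|
| (a) FVC 47.6%, ratio 0.80 | eligible | excluded |
| (b) FVC 47.6%, ratio 0.65 | excluded | excluded |
| (c) FVC 60%, ratio 0.80 | eligible | eligible |
| (d) FVC 51%, ratio 0.80 | eligible | eligible if FEV1 is also at least 50% |

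Case (d) depends on FEV1: at a predicted ratio of 0.85 it is 51 × 0.80 / 0.85 = 48.0%, and the revised rule would exclude on FEV1.

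**The case against.** The literal gap is hard to dispute, so the case on the other side concerns its consequence.

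- *Decline most naturally means an on-study fall.* On that reading a low baseline does not meet the stop, and the entry and stopping rules do not contradict each other. This is fair, but the numeric stop then offers such a participant nothing.
- *A level-based stop would rarely bite.* The only scheduled on-treatment PFT is at Week 12 or Early Termination, when study treatment is ending anyway. This is correct. It also makes screening the one scheduled check before exposure, which strengthens the case for a floor there.
- *Clinical judgement already protects.* Once an investigator judges that exclusion 7 is met, exclusion is mandatory. The chest X-ray, lung auscultation and, where available, DLCO inform that judgement. Section 5.1 allows stopping by investigator decision, and section 9.9.4 allows extra PFTs for dyspnea. This lowers the risk, but no PFT value obliges anyone to exclude.
- *The ratio condition may be deliberate.* It fits the airflow-obstruction subcategory in SAP 18.1.5. This is accepted, and the condition should stay. The same SAP category also covers reduced gas exchange, so the pulmonary concern is wider than obstruction.
- *It may be moot.* SAP sections 3.1 and 7 say the study will be discontinued early. The documents do not give enrolment status, so the recommendation has to be conditional.

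**Conclusion.** The concern holds. As written, exclusion 9 lets a participant with FEV1/FVC of 0.70 or above be randomised with FEV1, FVC or both already below 50% of predicted, and no other entry rule sets a numeric lung limit. Confidence in the logic is high; it rests on the plain reading of *and* in exclusion 9.

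The practical size is small. The pattern is probably rare and its frequency cannot be estimated from the documents. Investigator judgement reduces the risk, and the primary efficacy analysis is untouched. This is an inexpensive, optional safety improvement rather than a defect that threatens the trial.

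**What to change.** Only while enrolment is open: keep exclusion 9 and add, in the Synopsis and section 4.2, *or FEV1 or FVC < 50% of predicted at screening, regardless of FEV1/FVC ratio*.

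The cost is one clause in two places. No new test is needed, because every participant already has a screening PFT. The downside is that a few participants with a restrictive pattern become ineligible.

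The clause uses the protocol's own limit without a margin, so someone with both volumes at 51% remains eligible. A higher floor would be the sponsor's clinical choice. If enrolment has already ended early, no amendment is needed.

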5. REMOVAL OF PARTICIPANTS FROM STUDY TREATMENT OR ASSESSMENT

5.1. Discontinuation from Study Treatment

A participant's double-blind treatment may be discontinued for any of the following reasons:

- Adverse event that in the judgement of the Investigator and/or Medical Monitor indicate the participant should not continue study treatment
- Participant noncompliance with the protocol or study treatment that is considered significant by the Medical Monitor
- Investigator decision
- Withdrawal by participant
- Lack of efficacy
- Lost to follow-up
- Study termination by Sponsor
- Other, non-adverse event

A participant's double-blind treatment must be discontinued for any of the following reasons:

- Decline in PFT values (FEV₁ and/or FVC) below 50% of the predicted values
- Confirmed diagnosis of clinically significant macular edema
- Confirmed diagnosis of active TB
- Participants who have a cardiovascular treatment-related symptomatic event (eg, chest pain, dizziness, palpitations, lightheadedness, shortness of breath, or syncope) associated with reduction of the HR or associated with clinically relevant ECG changes at any time during the 4-hour monitoring period on Day 1 or Day 2 (as applicable) (Section 9.4.2.1)
- Participants who have not met the discharge criteria ([Table 3](#)) on Day 1 after \geq 4 hours of extended monitoring, or Day 2 by 4 hours postdose
- Pregnancy (Section 9.9.9)

- Suspected drug induced liver injury as defined by the 2009 FDA Guidance for Industry ([FDA 2009](#))
 - ALT or AST $> 8 \times$ ULN
 - ALT or AST $> 5 \times$ ULN for > 2 weeks
 - ALT or AST $> 3 \times$ ULN and (total bilirubin $> 2 \times$ ULN or international normalized ratio > 1.5)
 - ALT or AST $> 3 \times$ ULN with the appearance of fatigue, nausea, vomiting, right upper quadrant pain or tenderness, fever, rash, and/or eosinophilia ($> 5\%$)

Because transient fluctuations of ALT or AST are common, and progression to severe drug induced- liver injury or acute liver failure is uncommon, automatic discontinuation of study treatment upon finding a greater than $3 \times$ ULN elevation of ALT or AST may be unnecessary. If a drug induced-liver injury is identified, refer to Section [16.6](#) for guidance.

Participants who discontinue treatment prematurely, regardless of the reason, should be instructed to return for an ET visit within 7 days of the last administration of study treatment ([Table 6](#)) and complete all of the ET assessments. If a participant discontinues due to pregnancy, they are not required to complete the endoscopy. If the ET visit is within 4 weeks of the last sigmoidoscopy and biopsy, these procedures do not need to be repeated.

If the ET visit is ≥ 2 weeks after the last administration of study treatment, the 2-Week Follow-Up visit is not required; however, the 4-Week Follow-Up visit should be scheduled and completed. If the ET visit is ≥ 4 weeks of the last dose of study treatment, the 4-Week Follow-Up visit is not required unless the ALC is not within normal limits.

If treatment discontinuation is considered an adverse event, refer to Section [9.9.8.3.](#) for AE/SAE reporting guidance.

